11.5 Threshold Analysis Criteria

Table 11-6 Threshold Criteria for Clinical Chemistry and Hematology

Parameter	Threshold Criteria	Comments
Clinical Chemistry		
CPK	>ULN - ≤ 2.5 x ULN >2.5 - ≤ 5 x ULN >5 - ≤ 10x ULN >10 x ULN	CTCAE grades 1-4
Creatinine	>ULN - ≤ 1.5 x ULN >1.5 - ≤ 3.0 x ULN >3.0 - ≤ 6.0 x ULN >6.0 x ULN	CTCAE grades 1-4
Blood Urea Nitrogen	>ULN - ≤ 1.5 x ULN >1.5 - ≤ 3.0 x ULN >3.0 - ≤ 6.0 x ULN >6.0 x ULN	Same criteria as creatinine No CTCAE
Sodium	Hyponatremia <LLN - ≥130 mmol/L <130 - ≥120 mmol/L <120 mmol/L Hypernatremia >ULN - ≤ 150 mmol/L >150 mmol/L - ≤155 mmol/L >155 mmol/L - ≤ 160 mmol/L >160 mmol/L	CTCAE grade 1, 3, 4 (No CTCAE grade 2) CTCAE grade 1-4
Potassium	Hypokalemia <LLN - ≥ 3.0 mmol/L <3.0 - ≥ 2.5 mmol/L <2.5 mmol/L Hyperkalemia >ULN - ≤ 5.5 mmol/L >5.5 - ≤ 6.0 mmol/L >6.0 - ≤ 7.0 mmol/L >7.0 mmol/L	CTCAE grade 1&2, 3, 4 (Grade 1 and 2 are the same) CTCAE grade 1-4

Statistical Analysis Plan (Methods)
 Vertex Study: VX14-661-106

Total Cholesterol	>ULN - ≤ 7.75 mmol/L >7.75 - ≤ 10.34 mmol/L >10.34 - ≤ 12.92 mmol/L >12.92 mmol/L	CTCAE grade 1-4
Triglycerides	>1.71 - ≤ 3.42 mmol/L >3.42 - ≤ 5.7 mmol/L >5.7 - ≤ 11.4 mmol/L >11.4 mmol/L	CTCAE grade 1-4
Glucose	Hypoglycemia <3.0 - ≥ 2.2 mmol/L <2.2 - ≥ 1.7 mmol/L <1.7 mmol/L	CTCAE grade 1-4
	Hyperglycemia >ULN - ≤ 8.9 mmol/L >8.9 - ≤ 13.9 mmol/L >13.9 - ≤ 27.8 mmol/L >27.8 mmol/L	CTCAE grade 1-4
Albumin	<35 - ≥ 30 g/L <30 - ≥ 20 g/L <20 g/L	CTCAE grade 1-3
Amylase	>ULN - ≤ 1.5 x ULN >1.5 - ≤ 2.0 x ULN >2.0 - ≤ 5.0 x ULN >5.0 x ULN	CTCAE grade 1-4
Lipase	>ULN - ≤ 1.5 x ULN >1.5 - ≤ 2.0 x ULN >2.0 - ≤ 5.0 x ULN >5.0 x ULN	CTCAE grade 1-4
Direct bilirubin	>ULN - ≤ 1.5 x ULN >1.5 - ≤ 2 x ULN >2 - ≤ 3 x ULN >3 - ≤ 10 x ULN >10 x ULN	Same Criteria as Total Bilirubin No CTCAE Not in DILI Guidance
GGT	>ULN - ≤ 2.5 x ULN >2.5 - ≤ 5.0 x ULN >5.0 - ≤ 20.0 x ULN >20.0 x ULN	CTCAE grade 1-4
Calcium	Hypercalcemia	CTCAE grade 1-4

Statistical Analysis Plan (Methods)
 Vertex Study: VX14-661-106

	>ULN - \leq 2.9 mmol/L >2.9 - \leq 3.1 mmol/L >3.1 - \leq 3.4 mmol/L >3.4 mmol/L	
	Hypocalcemia <LLN - \geq 2.0 mmol/L <2.0 - \geq 1.75 mmol/L <1.75 - \geq 1.5 mmol/L <1.5 mmol/L	CTCAE grade 1-4
Magnesium	Hypermagnesemia >ULN - \leq 1.23 mmol/L >1.23 - \leq 3.30 mmol/L >3.30 mmol/L	CTCAE grade 1, 3, 4 No CTCAE grade 2
	Hypomagnesemia <LLN - \geq 0.5 mmol/L <0.5 - \geq 0.4 mmol/L <0.4 - \geq 0.3 mmol/L <0.3 mmol/L	CTCAE grade 1-4
Inorganic phosphate	Hypophosphatemia <0.74 - \geq 0.6mmol/L <0.6 - \geq 0.3 mmol/L <0.3 mmol/L	CTCAE grade 1-4
ALT	>ULN - \leq 3 xULN >3 - \leq 5 xULN >5 - \leq 8 xULN >8 - \leq 20.0 xULN >20.0 x ULN	Per FDA DILI Guidance Jul 2009 and CTCAE
AST	>ULN - \leq 3 xULN >3 - \leq 5 xULN >5 - \leq 8 xULN >8 - \leq 20.0 xULN >20.0 x ULN	FDA DILI Guidance and CTCAE
ALT or AST	(ALT>ULN and ALT \leq 3 xULN) or (AST>ULN and AST \leq 3 xULN) (ALT>3 xULN and ALT \leq 5 xULN) or	FDA DILI Guidance

Statistical Analysis Plan (Methods)
 Vertex Study: VX14-661-106

	(AST>3xULN and AST≤ 5 xULN) (ALT>5 xULN and ALT ≤ 8 xULN) or (AST>5xULN and AST≤ 8 xULN) (ALT>8 xULN and ALT ≤ 20 xULN) or (AST>8xULN and AST≤ 20 xULN) ALT>20 xULN or AST> 20 xULN	
Alkaline Phosphatase	>ULN - ≤ 1.5xULN >1.5 – ≤ 2.5 xULN >2.5 – ≤ 5.0 x ULN >5.0 – ≤ 20.0 x ULN >20.0 x ULN	FDA DILI Guidance and CTCAE
Total Bilirubin	>ULN - ≤ 1.5 x ULN >1.5 – ≤ 2 x ULN >2 – ≤ 3 x ULN >3 – ≤ 10 x ULN >10 x ULN	FDA DILI Guidance and CTCAE
ALT and Total Bilirubin	ALT>3xULN and TBILI>2xULN	FDA DILI Guidance Jul 2009
AST and Total Bilirubin	AST>3xULN and TBILI>2xULN	FDA DILI Guidance Jul 2009
(ALT or AST) and Total Bilirubin	(ALT>3xULN or AST>3xULN) and TBILI>2xULN	FDA DILI Guidance Jul 2009
Hematology		
WBC	WBC decreased <LLN - ≥ 3.0 x 10e9 /L <3.0 – ≥ 2.0 x 10e9 /L <2.0 – ≥ 1.0 x 10e9 /L <1.0 x 10e9 /L	CTCAE grade 1-4
	Leukocytosis >100 x 10e9 /L	CTCAE grade 3 (only Grade available)
Lymphocytes	Lymphocyte decreased <LLN - ≥ 0.8 x10e9 /L <0.8 – ≥ 0.5 x10e9 /L <0.5 – ≥ 0.2 x10e9 /L <0.2 x10e9 /L	CTCAE grade 1-4
	Lymphocyte increased >4 – ≤ 20 x10e9/L >20 x10e9/L	CTCAE grade 2, 3 (only Grades available)

Statistical Analysis Plan (Methods)
 Vertex Study: VX14-661-106

Neutrophils	Neutrophil decreased <LLN - $\geq 1.5 \times 10^9$ /L <1.5 - $\geq 1.0 \times 10^9$ /L <1.0 - $\geq 0.5 \times 10^9$ /L <0.5 $\times 10^9$ /L	CTCAE grade 1-4
Hemoglobin	Hgb decreased (anemia) <LLN - ≥ 100 g/L <100 - ≥ 80 g/L < 80 g/L	CTCAE grade 1-3
	Hgb increased >ULN - ≤ 20 g/L above ULN >20 g/L above ULN - ≤ 40 g/L above ULN >40 g/L above ULN	CTCAE grade 1-3
Platelets	Platelet decreased <LLN - $\geq 75.0 \times 10^9$ /L <75.0 - $\geq 50.0 \times 10^9$ /L <50.0 - $\geq 25.0 \times 10^9$ /L <25.0 $\times 10^9$ /L	CTCAE grade 1-4

Table 11-7 Threshold Criteria for Coagulation

Parameter	Threshold	Comments
Activated partial thromboplastin time (PTT)	>ULN - $\leq 1.5 \times$ ULN >1.5 - $\leq 2.5 \times$ ULN >2.5 x ULN	CTCAE grade 1-3
Prothrombin time (PT) International Normalized Ratio (INR)	>ULN - $\leq 1.5 \times$ ULN >1.5 - $\leq 2.5 \times$ ULN >2.5 x ULN	CTCAE grade 1-3

Table 11-8 Threshold Criteria for ECGs

Parameter	Threshold	Comments
HR	Bradycardia	Per HV grade 2, 3, plus shift change
	<50 bpm	
	<45 bpm	
	Decrease from baseline ≥ 10 bpm	
	Decrease from baseline ≥ 20 bpm	
	<50 bpm and decrease from baseline ≥ 10 bpm	
	<50 bpm and decrease from baseline ≥ 20 bpm	
	Tachycardia	Per HV grade 1, 2, 3, plus shift change
	>100 bpm	
	>115 bpm	
>130 bpm		
	Increase from baseline ≥ 10 bpm	
	Increase from baseline ≥ 20 bpm	
	>100 bpm and increase from baseline ≥ 10 bpm	
	>100 bpm and increase from baseline ≥ 20 bpm	
PR	≥ 240 ms	
	≥ 300 ms	
	≥ 200 ms and increase from baseline ≥ 40 ms	
	≥ 200 ms and increase from baseline ≥ 100 ms	
QRS	>110 ms	
	>160 ms	
	Increase from baseline ≥ 20 ms	
	Increase from baseline ≥ 40 ms	
QTc	>450 ms (Male)	
	>470 ms (Female)	
	≥ 500 ms	
	Increase from baseline >10 ms	
	Increase from baseline >20 ms	
	Increase from baseline >40 ms	
	Increase from baseline >60 ms	

Table 11-9 Threshold Criteria for Vital Signs

Parameter	Threshold Criteria	Comments
HR	Same PCS as above in ECG category	
SBP	SBP increased >140 mmHg >160 mmHg >10 mmHg increase from baseline >20 mmHg increase from baseline >140 mmHg & >10 mmHg increase from baseline >140 mmHg & >20 mmHg increase from baseline >160 mmHg & >10 mmHg increase from baseline >160 mmHg & >20 mmHg increase from baseline	809/770 analyses
	SBP decrease <90 mmHg <80 mmHg >10 mmHg decrease from baseline >20 mmHg decrease from baseline <90 mmHg and >10 mmHg decrease from baseline <90 mmHg and >20 mmHg decrease from baseline <80 mmHg and >10 mmHg decrease from baseline <80 mmHg and >20 mmHg decrease from baseline	Per HV grade 1, 3, plus shift change

DBP	DBP increased	809/770 analyses
	
 >90 mmHg >100 mmHg >5 mmHg increase from baseline >10 mmHg increase from baseline >90 mmHg and >5 mmHg increase from baseline >90 mmHg and >10 mmHg increase from baseline >100 mmHg and >5 mmHg increase from baseline >100 mmHg and >10 mmHg increase from baseline 	
	DBP decreased	
	
 <60 mmHg <45 mmHg >5 mmHg decrease from baseline >10 mmHg decrease from baseline <60 mmHg and >5 mmHg decrease from baseline <60 mmHg and >10 mmHg decrease from baseline <45 mmHg and >5 mmHg decrease from baseline <45 mmHg and >10 mmHg decrease from baseline 	
Weight	Weight gain	CTCAE grade 1-3
	
 ≥5 % increase from baseline ≥10 % increase from baseline ≥ 20% increase from baseline 	
	Weight loss	CTCAE grade 1-3
	
 ≥5 % decrease from baseline ≥10 % decrease from baseline ≥ 20% decrease from baseline 	

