11.7.7 Liver Function Test Parameters

Liver Function Testing

Liver function testing (ALT, AST, GGT, ALP, direct bilirubin, and total bilirubin) must be performed as noted in Table 3-2 for serum chemistry, while subjects are receiving study drug treatment and at the Safety Follow-up Visit. These blood samples should be processed and shipped immediately per the Laboratory Manual.

Subjects with new treatment-emergent ALT or AST elevations of $>3 \times$ ULN and clinical symptoms must be followed closely, including repeat confirmatory testing performed by the central laboratory within 48 to 72 hours of the initial finding and subsequent close monitoring of ALT and AST levels, as clinically indicated. In addition, if ALT or AST is $>5 \times$ ULN, repeat follow-up levels must be obtained within 7 ± 2 days.

If a subject cannot return to the site for liver function testing, a local laboratory may be used. Elevations in LFTs at the local laboratory must be reported immediately to the medical monitor, and the subject must have the tests repeated and sent to the central laboratory as soon as possible (ideally within 48 to 72 hours).

Study Drug Interruption

Study drug administration **must be interrupted** immediately (prior to confirmatory testing), and the medical monitor must be notified, if any of the following criteria is met:

- ALT or AST $>8 \times$ ULN
- ALT or AST $>5 \times$ ULN for more than 2 weeks
- ALT or AST $>3 \times$ ULN, in association with total bilirubin $>2 \times$ ULN and/or clinical jaundice

A thorough investigation of potential causes should be conducted and the subject should be followed closely for clinical progression.

If no convincing alternative etiology (e.g., acetaminophen use, viral hepatitis, or alcohol ingestion) for the elevated transaminases is identified, regardless of whether ALT or AST levels have improved, study drug treatment must be permanently discontinued if repeat testing within 48 to 72 hours confirms the initial elevation. Subjects in whom treatment is discontinued for elevated transaminases should have their transaminases monitored closely until levels normalize or return to baseline.

Resumption of Study Drug

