8.4.2 Clinical Laboratory Values

For treatment emergent laboratory measurements, the raw values and change from baseline values for the continuous hematology, chemistry and coagulation results will be summarized in SI units by treatment group at each scheduled time point. For hematology, chemistry and coagulation, the number and percentage of subjects with an abnormal low (<LLN) value and with an abnormal high (>ULN) value at each scheduled time point will be summarized.

The number and percentage of subjects with hematology, chemistry and coagulation values meeting the defined threshold criterion will be summarized by treatment, lab parameters, and visit. The threshold criteria are provided in Section 11.5, Table 11-6 and Table 11-7.

For all LFT results (alanine aminotransferase [ALT], aspartate aminotransferase [AST], alkaline phosphatase [ALP], direct bilirubin, total bilirubin, and gamma-glutamyl transferase [GGT]), the following additional analyses will be conducted:

- A listing of subjects with elevated LFT results during the TE period will be presented. For each subject in the listing, LFT assessments at all visits will be included.
- For each of the LFTs, mean values (\pm SD) will be plotted by visit, and a box plot of the LFT value/ULN will be plotted by visit.
- The incidence of LFTs meeting threshold criteria against the baseline threshold criteria also will be summarized by treatment group, LFT parameters, and visit (only shifts to values worse than baseline will be presented).
- A scatter plot of the maximum ALT value across visits versus the maximum total bilirubin value also will be presented. The ALT and total bilirubin values will be presented on a logarithmic scale. The graph will be divided into 4 quadrants with a vertical line corresponding to 3xULN for ALT and a horizontal line corresponding to 2xULN for total bilirubin. A similar graph of maximum AST value versus maximum total bilirubin value will be presented as well.

A summary table for the shift from baseline to the value at Week 24 will be presented by treatment group for vitamin levels and lipid panel. A box plot of vitamin levels and lipid panel also will be plotted against visit.

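### The combined ALT-or-AST bands in SAP Table 11-6 overlap, so the number of subjects above 3, 5 or 8 x ULN can in general only be bounded from the table

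*SAP*

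**What the plan says.** SAP section 11.5, Table 11-6, grades ALT and AST separately and then adds a combined ALT-or-AST parameter with five rows: above ULN to 3, above 3 to 5, above 5 to 8, above 8 to 20, and above 20 x ULN. Each closed row is met when either enzyme lies in that interval. Two of them read "ALT>5 xULN and ALT ≤ 8 xULN) or (AST>5xULN and AST≤ 8 xULN" and "ALT>8 xULN and ALT ≤ 20 xULN) or (AST>8xULN and AST≤ 20 xULN". The top row is open-ended: "ALT>20 xULN or AST> 20 xULN". The only other combined row without an upper limit on the enzymes also requires raised bilirubin: "ALT>3xULN or AST>3xULN) and TBILI>2xULN".

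SAP section 8.4.2 says how the table is filled: the number and percentage of subjects with values "meeting the defined threshold criterion will be summarized by treatment, lab parameters, and visit". It has no rule for a subject who meets two rows of one parameter. SAP section 8.4.1.5 does have such a rule for adverse events, which are counted once at the worst severity.

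Protocol section 11.7.7 uses open-ended limits on either enzyme:
- >5 x ULN leads to repeat levels.
- >8 x ULN leads to interruption.
- "ALT or AST $>5 \times$ ULN for more than 2 weeks" also leads to interruption.
- >3 x ULN counts only with clinical symptoms, or with total bilirubin >2 x ULN and/or jaundice.

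**The concern.** Graded rows for one parameter are normally read as a partition: each subject appears once at a visit, and the number above a limit is the sum of the rows above it. The separate ALT and AST rows work that way. The combined rows do not, because a subject whose enzymes are both above ULN but in different bands appears in two of them.

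A safety reader will want the number of subjects with either enzyme above 3, 5 or 8 x ULN. Raised transaminases are a named safety topic in the SAP (sections 8.4.1.7 and 8.4.1.8), and 5 and 8 x ULN are limits on which the protocol acts without a further condition. No combined row gives these counts directly, and adding the rows can overstate them.

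**Working it through.** The documents state no count on this point, so there is no figure to reproduce. The check is logical.

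**Inputs.** The five combined rows of SAP Table 11-6 and the per-visit subject count of SAP section 8.4.2. Write a = ALT/ULN and b = AST/ULN for one subject at one visit. A combined row is met if a or b lies in its band.

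**Step 1: how many rows one subject can meet.** Each enzyme is at or below ULN or in one of five bands, so there are 6 x 6 = 36 pairs.
- No row: both at or below ULN, 1 pair.
- One row: both above ULN in the same band (5 pairs), or exactly one above ULN (5 + 5 = 10 pairs), 15 in all.
- Two rows: both above ULN in different bands, 5 x 5 − 5 = 20 pairs.

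The total is 1 + 15 + 20 = 36, and two rows is the maximum at one visit. These are combinations, not expected frequencies. With a = 9 and b = 4, the subject meets the above-8-to-20 row and the above-3-to-5 row.

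**Step 2: what the sum of rows measures.** Fix a limit t of 3, 5 or 8. Let A and B be the numbers with ALT and AST above t, J the number with both above t, and C the number with both above t in the same band.
- True number with either enzyme above t: N = A + B − J.
- Sum of the combined rows above t: S = A + B − C.
- Excess: S − N = J − C, the number with both enzymes above t but in different bands.

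A, B and S can be read from the table, and C follows from them. J cannot. So N is at least the largest contributing row and at most S. The separate rows can raise the lower bound to the larger of A and B, but they do not identify N.

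**Step 3: proof by example.** In each line the two data sets, two subjects each as (a, b), give identical ALT rows, AST rows and combined rows.

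| Limit | First data set | Second data set | True number above limit | Sum of combined rows |
|---|---|---|---|---|
| >3 | (6, 4), (0.5, 0.5) | (6, 0.5), (0.5, 4) | 1 versus 2 | 2 in both |
| >5 | (10, 6), (0.5, 0.5) | (10, 0.5), (0.5, 6) | 1 versus 2 | 2 in both |
| >8 | (25, 10), (0.5, 0.5) | (25, 0.5), (0.5, 10) | 1 versus 2 | 2 in both |

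The number above 20 x ULN agrees within each pair, because that row is open-ended.

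**Step 4: when the count can still be read.** If no subject has both enzymes above t in different bands, then J = C and S = N. For example, if the above-20 row is empty, the number above 8 x ULN equals the above-8-to-20 row.

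**Step 5: after the change.** Classing on max(a, b) puts (6, 4) in the above-5-to-8 band only. The number above 3 x ULN is then 1, where the rows as written sum to 2.

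**The case against.** **The rows are not wrong as stated.** Each counts subjects with either enzyme in the band, and the SAP neither sums them nor says that they partition subjects. Overlapping criteria also appear elsewhere in the appendix, such as heart rate below 50 and below 45 bpm, or systolic pressure above 140 and above 160 mmHg. The first part stands: double counting arises only when a reader adds rows. The comparison is weaker. Those criteria are nested and open-ended, so each gives its count directly. The combined transaminase bands are closed, so adding is the only route to a count above 3, 5 or 8 x ULN.

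**The values are available elsewhere.** SAP section 8.4.2 plans a listing of subjects with elevated liver tests showing all visits, and plots of maximum ALT and maximum AST against maximum bilirubin. This stands. The counts can be recovered from the listing, so nothing is lost but a usable summary. Safety analyses are descriptive with no testing (SAP section 8.4), so no inference is affected.

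**Protocol triggers.** A reader might infer that the table fails to reproduce the protocol's liver rules as a whole. The documents do not support that. Most rules also need symptoms, jaundice, bilirubin or duration. The rule of >3 x ULN with bilirubin >2 x ULN has its own row; symptoms, jaundice and duration are not in this table at all. Only >5 x ULN for repeat testing and >8 x ULN for interruption are bare limits.

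**Shift summary.** A reader might also infer that the baseline comparison in SAP section 8.4.2 ("The incidence of LFTs meeting threshold criteria against the baseline threshold criteria also will be summarized") becomes ambiguous. That section lists the tests concerned: ALT, AST, ALP, direct and total bilirubin, and GGT. The combined parameter is not among them, and each listed test has mutually exclusive bands.

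**Conclusion.** The point holds as a minor defect of one descriptive table. At a visit, any subject with both enzymes above ULN in different bands is counted in two combined rows. The number with ALT or AST above 3, 5 or 8 x ULN is then only bounded, unless no subject has both enzymes above the limit in different bands. The excess in the summed rows equals the number of such subjects.

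The documents give no information on how often ALT and AST fall in different bands, so a percentage overstatement cannot be supported; it could be zero. The conclusion assumes that the table is programmed as written, with no unstated worst-category rule. It concerns tabulation only and makes no judgement on any clinical limit.

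**What to change.** In SAP Table 11-6, define the combined bands on the larger of ALT/ULN and AST/ULN from the same sample, so that each subject with either enzyme above ULN falls in exactly one band per visit. Add open-ended rows for ALT or AST >3, >5 and >8 x ULN, and state the derivation in a footnote. The bilirubin rows stay as they are.

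The cost is one derived variable, three rows and a footnote. Data collection and clinical limits are unchanged. The change does not add the protocol's symptom, jaundice or duration conditions to the table.

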11.6 Standards for Efficacy and Safety Variable Display in TFLs

Table 11-10 Precision Standards for Efficacy Variables

Variable	Statistics	Number of Decimal Places
ppFEV ₁ (% absolute or relative change)	Mean, LS mean, 95% CI	1
FEV ₁ (L, absolute or relative change)	Mean, LS mean, 95% CI	2
FEF, FVC	Mean, LS mean, 95% CI	2
CFQ-R	Mean, LS mean, 95% CI	1
Sweat chloride (mmol/L)	Mean, LS mean, 95% CI	1
BMI (kg/m ²)	Mean	2
	LS mean, 95% CI	2
BMI-for-age z-score	Mean, LS mean, 95% CI	2
Weight (kg)	Mean	1
	LS mean, 95% CI	1
Weight-for-age z-score	Mean, LS mean, 95% CI	2
Time-to-first clinical event of interest, e.g., pulmonary exacerbation	Proportion of event-free, 95% CI	3
	Hazard ratio (HR), 95% CI for HR	2

Normalized days with pulmonary exacerbations

Mean	1
Number of events	0
Event rate	2

Number of decimal places for standard error and standard deviation will be the same as for the corresponding mean.

Table 11-11 Standard Display Units in Percent Predicted FEV1

Variable	Unit	Displayed Unit
ppFEV ₁	percent	N/A
Absolute change in ppFEV ₁	percent	Percentage points
Relative change in ppFEV ₁	percent	%

11.7 Imputation Rules for Missing AE Start Date

For missing or partial AE start date, use the imputation rules below.

If only Day of AE start date is missing:

If the AE start year and month are the same as that for the first dose date, then:

If the full (or partial) AE end date is NOT prior to the first dose date or AE end date is missing, then impute the AE start day as the day of first dose date; otherwise, impute the AE start day as 1.

Otherwise, impute the AE start day as 1.

Compare the imputed AE start date with TE period to determine whether the AE is pre-treatment AE, TEAE or post-treatment AE.

If Day and Month of AE start date are missing:

If AE start year = first dose year, then:

If the full (or partial) AE end date is NOT prior to the first dose date or AE end date is missing, then impute the AE start Month and Day as the Month and Day of first dose date; otherwise, impute the AE start Month as January and the Day as 1.

Otherwise, impute the AE start Month as January and the Day as 1.

Compare the imputed AE start date with TE period to determine whether the AE is pre-treatment AE, TEAE or post-treatment AE.

If Year of AE start date is missing:

If the year of AE start is missing or AE start date is completely missing then query site with no imputation. Also compare the full (or partial) AE end date to the first dose date. If the AE end date is prior to the first dose date then the AE should be considered as a pre-treatment AE. Otherwise, the AE will be considered as TEAE.
